14.6.2 ECG

QT interval data will be presented using Bazett's (QTcB) and Fridericia's (QTcF) corrections.

ECG data will be summarised by treatment and time point. Differences from baseline (Day 0 pre-dose) will be summarised by treatment and time point.

The number of subjects with a potentially clinically important ECG value will be summarised by actual treatment and time point, giving the numbers of subjects with QT, QTcB or QTcF > 450 msec, > 480 msec and > 500 msec, and the numbers of subjects with increases in QT, QTcB or QTcF from baseline of > 30 msec and > 60 msec³. A supporting listing of all subjects with an ECG value of potential clinical importance and a separate listing of ECG findings classified as abnormal by the Investigator will also be provided.

14.6.3 Physical and neurological examination

Abnormal physical and neurological examination findings will be listed.

15 Pharmacokinetic Analyses

Analytical Services International Ltd, London, U.K will measure the plasma concentrations of emodepside. The pharmacokinetic analysis will be done by HMR. Pharmacokinetic parameters will be calculated using WinNonlin, version 7 or higher.

The pharmacokinetic parameters to be derived are given in Appendix B.

PK Concentration data will be summarised using the PK concentration population. PK parameters will be summarised using the PK Parameter population.

For log normally distributed parameters, the primary measure of central tendency will be the geometric mean⁴; for other parameters, it will be the arithmetic mean or median.

For all variables N (number of subjects receiving the treatment/formulation in the population), n (number of observations), arithmetic mean, median, minimum, maximum, SD, %CV, and the 95% confidence interval for the arithmetic mean will be provided. For log-transformed variables, all of the above plus the geometric mean, which is the anti-logged arithmetic mean of log-transformed variables, its 95% confidence interval and the SD of the logs will be provided.

The between-subject CV will be calculated using:

1. $\%CVb = 100 * (\text{SD}/\text{Mean})$ with SD and Mean of untransformed data
2. $\%CVb = 100 * \sqrt{(\exp(\text{SD})^2 - 1)}$ with SD of log-transformed data

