vision, photophobia (“Increased ocular light sensitivity”), visual impairment (“distorted contrast perception”, “distorted colour perception”) reported by 8 out of 47 subjects receiving emodepside were considered as treatment-related by the Investigator. Also of note, at the highest dose (40 mg), lightheadedness (n=1), dizziness (n=1) or headache (n=1) were reported concomitantly to blurred vision.

None of the volunteers met any of the protocol-specified withdrawal criteria with regards to treatment and overall tolerability to emodepside has been acceptable up to 20 mg. The presence of post-dose visual disturbances in subjects of Cohort 8 receiving either 40 mg solution or placebo may warrant some concern and escalation was stopped at this dose level.

The pharmacokinetic results obtained so far show that T_{max} for the LSF solution is consistently about 1 h post-dose when fasted. Mean C_{max} and AUC for the LSF solution have been roughly dose-proportional, with low to moderate inter-individual variability. The plasma half-life during the first 24 h is very short for a single dose of emodepside. After 3, 7, 16 and 47 h the maximum plasma concentration is reduced to 50%, 25%, 12.5% and 6.25% respectively. Terminal plasma half-life is 523 h. Although data of Cohort 9 (which was treated with a single dose of emodepside with food) are still under review, administration of the LSF of 10 mg with a high fat, high-calorie meal resulted in a clinically relevant food effect with a reduction of AUC to ~67%, C_{max} to 42% and a delay of the T_{max} up to 2.33 h. Therefore, the recommendation of administration of the emodepside (LSF) under fasted conditions is given.

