In the FIH study, single doses of 5 and 10 mg emodepside, administered as LSF oral solution in the fasted state, were safe and well tolerated. Since those doses are likely to fall within the dose range tested in later phase studies, and have previously been well tolerated in healthy volunteers, they have been selected for this relative bioavailability study. It is anticipated that emodepside exposure following IR-tablets (in both fasted and fed states) will be no higher than exposure following the same dose of LSF oral solution. Anticipated exposures for each formulation tested in this study are provided below.

Following a single dose of 5 mg emodepside, administered as LSF oral solution in the FIH study, mean \pm SD (CV%) C_{max} was 93.2 ± 15.7 ng/mL (16.8%) and AUC_{last} was 1736.2 ± 392.5 ng \cdot h/mL (22.6%). Exposures in Part 1 of this study are likely to be similar to, or lower than, these values.

Following a single dose of 10 mg emodepside, administered as LSF oral solution in the FIH study, mean \pm SD (CV%) C_{max} was 178.6 ± 47.9 ng/mL (26.8%) and AUC_{last} was 3165.2 ± 817.2 ng \cdot h/mL (25.8%). Exposures in Part 2 of this study are likely to be similar to, or lower than, these values.

The highest single dose which has been shown to be well tolerated is 20 mg LSF oral solution, which resulted in mean \pm SD (CV%) C_{max} of 315.7 ± 87.6 ng/mL (27.7%) and AUC_{last} of 7617.0 ± 1467.7 ng \cdot h/mL (19.3%). Even if exposures in Parts 1 and 2 are higher than anticipated, they are unlikely to exceed these values.

Therefore, the proposed doses to be tested in this study are considered acceptable.

4. Selection of Subjects

The following eligibility criteria were designed to select subjects for whom the protocol treatment is considered appropriate. All relevant medical and non-medical conditions should be taken into consideration when deciding whether this protocol is suitable for a particular subject. Eligibility criteria may not be waived by the Investigator. Any questions regarding a subject's eligibility should be discussed with DNDI Medical Monitor before the subject's enrolment.

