Parameter	Treatment (N=xx)	n	Mean	95% CI	SD	%CVb	Median	Min	Max
AUC _{last} (units)									
C _{max} (units)									

Source: Listing 16.2.xx

Programming notes: *Continued with all dose levels and parameters*

Template T_PK4

Table 14..2.xx Summary of Log-Transformed Derived Emodepside Plasma Pharmacokinetic Parameters

Parameter	Treatment (N=xx)	n	Geom Mean	95% CI	SD (logs)	%CVb
AUC _{last} (units)						
C _{max} (units)						

Source: Listing 16.2.xx

Programming notes: Continued with all dose levels and parameters

Template T_PK6

Table 14.2.xx Summary of Relative Bioavailability of Emodepside

Parameter	Test Formulation	Reference	LSMeans		Test vs Reference	
			Test	Ref	Ratio (%)	90% CI
C _{max} /Dose (units)	#406 5 mg	LSF	xx.x	xx.x	xxxx.x	xxxx.x, xxxx.x
	#416 5 mg		xx.x	xx.x	xxxx.x	xxxx.x, xxxx.x
AUC _{0-7d} /Dose (units)	#406 5 mg	LSF	xx.x	xx.x	xxxx.x	xxxx.x, xxxx.x
	#416 5 mg		xx.x	xx.x	xxxx.x	xxxx.x, xxxx.x

Source: Listing 16.2.xx

Programming notes:
 For bioavailability In part 1a calculate values for "B/A" and "C/A"
 In part 2 calculate values for "F/A" and "G/A"
 For food effect calculate for part 1 only values for "D/B" and "E/C"

Template T_PK8

Table 14.2.xx Summary of Dose Proportionality Analysis of Emodepside

10mg vs 5 mg			
Formulation	Parameter	Ratio (%)	95% CI
#406 5 mg	C_{max} (units)	xxxx.x	xxxx.x, xxxx.x
	AUC_{0-7d} (units)	xxxx.x	xxxx.x, xxxx.x

Source: Listing 16.2.xx

Programming notes: Continue with all formulations. Calculate "F/B" and/or "G/C"

Template T_AE1

Table 14.3.3.xx Summary of Treatment-Emergent Adverse Events

System Organ Class	Preferred Term	Treatment 1 (N=xx)	Treatment 2 (N=xx)	Etc
		n (%)	n (%)	
Number of subjects with AEs		x (xx.x)	x (xx.x)	
Gastrointestinal disorders	Total number of subjects	x (xx.x)	x (xx.x)	
	Abdominal discomfort	x (xx.x) [xx]	x (xx.x) [xx]	
	Abdominal pain	x (xx.x) [xx]	x (xx.x) [xx]	
		↓		
Nervous system disorders	Total number of subjects			
	Dizziness			
	Headache			
		↓		
		↓		

n = number of subjects (subjects with ≥ 1 adverse event are counted only once per system organ class and preferred term)

[] = number of adverse events

Based on MedDRA version xx.x

Source: Listing 16.2.xx

Programming notes: Continued with all treatment groups

SOCs and PTs are sorted in decreasing order of frequency

Presented for all applicable MedDRA system organ classes and terms.

Template T_LB1

Table 14.3.4.xx Summary of Laboratory Values of Potential Clinical Importance

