2.1 Derived and transformed data

In general, concentration and concentration-related quantities, rate constants and half-lives (e.g. C_{\max} , AUC, $t_{1/2}$ and MRT) will be analysed after logarithmic transformation. Logarithmic transformations will use natural logarithms (\log_e). A list of those parameters that will be log transformed are given below.

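### SAP section 15: the %CVb formula for log-transformed PK parameters squares the exponential instead of the SD, overstating the CV about 3.1- to 3.7-fold at the first-in-human CVs

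*SAP*

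**What the plan says.** SAP section 15 introduces two formulas with the words "The between-subject CV will be calculated using":

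- Item 1, for untransformed data, is `100 * (SD/Mean)`.
- Item 2, to be used "with SD of log-transformed data", is `100 * sqrt(exp(SD)^2 - 1)`, with the square after the closing bracket of `exp(SD)`.

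SAP Appendix B 2.1 fixes the base of the logs: "Logarithmic transformations will use natural logarithms". Appendix B 3.1.1 marks 11 parameters for log transformation: Cmax, Cmax/Dose, Cmax,norm, λz, two half-lives, AUClast, AUC0-7d, AUC0-7d/Dose, AUC0-7d,norm and MRTlast. The four primary-endpoint parameters are among them.

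Table 14.2.3 uses template T_PK4, titled "Summary of Log-Transformed Derived Emodepside Plasma Pharmacokinetic Parameters". Its columns are n, geometric mean, 95% CI, SD (logs) and %CVb. Table 14.2.2 (template T_PK3), for the untransformed parameters, also has a column headed %CVb.

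Protocol 11.7 asks for %CV but gives no formula, and neither does Appendix B. Section 15 of the SAP is the only specification.

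**The concern.** For log-normal data analysed on the natural-log scale, the CV follows from the log-scale SD by an identity, `sqrt(exp(SD^2) - 1)`. It is not a choice between methods. Item 2 as it reads is a different quantity, and at ordinary levels of variability a much larger one.

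A program written to item 2 would have two visible effects:

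- In Table 14.2.3, %CVb would not reconcile with SD (logs) in the same row.
- Tables 14.2.2 and 14.2.3 would show very different values under the same heading for the same parameter and arm.

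Protocol 1.4 describes the first-in-human results for the solution as having Cmax and AUC "with low to moderate inter-individual variability". Comparable data run through item 2 would appear highly variable. Anyone taking a between-subject CV from Table 14.2.3 to plan a later parallel-group study of these tablets would start from a figure about three times too large.

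**Working it through.** **Inputs.** Protocol 3.4 gives first-in-human means, SDs and CVs for the fasted solution at 5, 10 and 20 mg. These are the only numerical CVs in the documents.

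**Step 1: reproduce the stated CVs as 100 × SD/mean.**

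- Cmax: 15.7/93.2 = 16.85%, 47.9/178.6 = 26.82%, 87.6/315.7 = 27.75%.
- AUClast: 392.5/1736.2 = 22.61%, 817.2/3165.2 = 25.82%, 1467.7/7617.0 = 19.27%.

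All agree with the stated values to within 0.05 points.

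**Step 2: convert each CV to a log-scale SD**, assuming log-normal data: `s = sqrt(ln(1 + CV^2))`.

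**Step 3: apply both formulas.** For 5 mg AUClast:

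- `s = sqrt(ln(1 + 0.226^2)) = 0.2232`
- As written: `100 * sqrt(exp(2 * 0.2232) - 1) = 75.0%`
- Log-normal: `100 * sqrt(exp(0.2232^2) - 1) = 22.6%`

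| First-in-human result | s | Log-normal CV | Item 2 as written | Ratio |
|---|---|---|---|---|
| 5 mg Cmax | 0.1668 | 16.8% | 62.9% | 3.75 |
| 5 mg AUClast | 0.2232 | 22.6% | 75.0% | 3.32 |
| 10 mg Cmax | 0.2634 | 26.8% | 83.3% | 3.11 |
| 10 mg AUClast | 0.2539 | 25.8% | 81.3% | 3.15 |
| 20 mg Cmax | 0.2719 | 27.7% | 85.0% | 3.07 |
| 20 mg AUClast | 0.1912 | 19.3% | 68.3% | 3.54 |

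Taking the CV itself as the log SD, without the conversion, gives ratios of 3.05 to 3.74, so the result does not depend on step 2.

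**Step 4: range for parameters without a stated CV.** The documents give no CV for tablets #406 or #416, the fed state, AUC0-7d, half-life or MRT. For assumed true CVs:

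| Assumed true CV | Item 2 as written | Ratio |
|---|---|---|
| 10% | 47.0% | 4.7 |
| 14.4% | 57.6% | 4.0 |
| 29.4% | 88.2% | 3.0 |
| 40% | 107.7% | 2.7 |
| 60% | 142.5% | 2.4 |

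The ratio falls as variability rises. The two formulas agree at s = 2, and above that the written one is too low. The first-in-human values of s are 0.17 to 0.27.

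**Step 5: could ordinary sampling differences explain such a gap?** Items 1 and 2 differ somewhat in small samples even when both are right. In 200,000 simulated log-normal samples of n = 12 with a true CV of 22.6%, the correct item 2 lay within 3.0 points of item 1 in 95% of samples. Item 2 as written exceeded item 1 by a median of 51.7 points (95% range 41.6 to 62.8). With n = 10 the figures were 3.2 points and a median of 51.6 (40.4 to 63.9).

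**The case against.** The strongest objection is provenance. The point rests on the position of one superscript in text that a program read from a PDF, and such text can be damaged at character level. The sponsor's page may show exp(SD²), and repeating the arithmetic on the same text cannot settle that. This stands as a caveat, and it is why the original page has to be checked. It does not remove the point, because the text as available specifies the wrong quantity and no other part of the SAP or protocol corrects it.

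The second objection is consequence. No decision rule, sample-size calculation or Part 2 selection criterion refers to %CVb. Table 14.2.3 prints SD (logs) beside it, so the right value can be recovered, and Table 14.2.2 gives a valid arithmetic CV. This also stands and limits the effect to one descriptive column. It does not justify leaving a formula that gives wrong numbers in a planned table for the primary parameters.

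Third, the size rests on another study: the solution only, groups of about five or six subjects, and AUClast rather than AUC0-7d. That is fair, and the assumed range in the working covers it; the overstatement is at least 2.4-fold for any true CV up to 60%. The first-in-human description of variability is context only. It sets no threshold and does not contradict the SAP.

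**Conclusion.** The concern holds. Item 2 of the CV formulas in SAP section 15, as it reads, is not the between-subject CV. At the first-in-human CVs of 16.8% to 27.7% it would print 62.9% to 85.0%. The size assumes log-normal data and variability similar to the first-in-human study; the direction holds for any log-scale SD below 2. The algebra is certain. That the sponsor's own page carries the same formula is likely but needs confirming. No inferential result is affected, so this should be fixed but does not threaten the trial's conclusions.

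**What to change.** Replace item 2 in SAP section 15 with `%CVb = 100 * sqrt(exp(SD^2) - 1)`, and state that SD is the standard deviation of the natural-log values. Check the original SAP page and the T_PK4 program against this before Table 14.2.3 is produced. If the page and program are already right, nothing more is needed.

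The cost is a one-line SAP correction and one program check. No other analysis changes.

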15.1 Pharmacokinetic Concentration Data

The plasma concentrations will be listed and summarised by treatment. Individual and mean plasma concentration–time profiles will be presented graphically.

15.2 Pharmacokinetic Parameters

The pharmacokinetic parameters will be listed and summarised by treatment.

To assess the relative bioavailability, analysis of variance (ANOVA) models will be fitted to the tablet (test) and solution (reference) data with the logarithm of the pharmacokinetic parameters $AUC_{0-7d}/Dose$ or $C_{max}/Dose$ as the dependent variable, and formulation as a fixed effect. The point estimates least squares (LS)-means and 90% confidence intervals for the ratios “B/A” and “C/A” will be calculated in Part 1a. In Part 2, “F/A” and/or “G/A” will be calculated. The acceptance range 80 – 125% will be applied for these assessments.

In part 1, to assess the effect of food, ANOVA models will be fitted to the data with the logarithm of the pharmacokinetic parameters $AUC_{0-7d}/Dose$ or $C_{max}/Dose$ as the dependent variable, and fed (test) or fasted (reference) as a fixed effect. The point estimates and 90% confidence intervals for the ratios “D/B” and “E/C” will be calculated. The acceptance range 80 – 125% will be applied for the assessment of a potential food effect.

To assess dose proportionality, for each tablet type, exploratory ANOVA models will be fitted to the relevant fasted data in Parts 1 and 2 with the logarithm of the pharmacokinetic parameters AUC_{0-7d} or C_{max} as the dependent variable and dose as a fixed effect. The ratios “F/B” and/or “G/C” will be calculated, with their 95% confidence interval.

16 References

1. International Conference on Harmonization, 1998. Statistical Principles for Clinical Trials - ICH Harmonised Tripartite Guideline. Guidance for Industry, E9, FDA federal register, Vol 63, 1998, p49583. Available at: <http://www.fda.gov/cder/guidance>.
2. International Conference on Harmonization, 1995. Structure and Content of Clinical Study Reports - ICH Harmonised Tripartite Guideline. Guidance for Industry, E3, FDA federal register, Vol 61, 1996, p37320. Available at: <http://www.fda.gov/cder/guidance>.
3. International Conference on Harmonisation, 2005. Clinical Evaluation of QT/QTc Interval Prolongation and Proarrhythmic Potential for Non-Antiarrhythmic Drugs. Concept paper, Guidance for Industry, E14, Center for Drug Evaluation and Research (CDER). Available at: <http://www.fda.gov/cder/guidance/6922fnl.htm>.
4. Julious, SA & Debarnot, CAM (2000) “Why are Pharmacokinetic Data Summarised by Arithmetic Means?”, Journal of Biopharmaceutical Statistics, 10 (1), p55-71

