3.1. Study design

This is a single-centre, open-label, randomized, parallel-group relative bioavailability study in healthy men. The study will be done in 2 parts, as follows:

- Part 1 – single oral doses of 5 mg emodepside will be tested:
 - Part 1a – the LSF (reference formulation) and 2 new IR-tablet formulations (test formulations) will be administered in the fasted state.
 - Part 1b – the 2 new IR-tablet formulations will be administered in the fed state (high-fat, high-calorie meal).
- Part 2 – single oral doses of 10 mg emodepside will be tested: depending on the results from Part 1, one or both IR-tablet formulations will be administered in the fasted state.

The treatments in each study part are summarised in Table 1.

Table 1. Planned treatments by dose, formulation and condition

Part	Treatment	Formulation, dose and condition	Number of subjects
Part 1a	A	5 mg emodepside LSF, fasted	12
	B	5 mg emodepside IR-tablet #406, fasted	12
	C	5 mg emodepside IR-tablet #416, fasted	12
Part 1b	D	5 mg emodepside IR-tablet #406, fed	12
	E	5 mg emodepside IR-tablet #416, fed	12
Part 2	F*	2 x 5 mg emodepside IR-tablet #406, fasted	12
	G*	2 x 5 mg emodepside IR-tablet #416, fasted	12

* one or both treatments may be tested, depending on results from Part 1

Up to 84 healthy volunteers will be enrolled, in up to 7 treatment arms made up of 12 subjects each.

The 36 subjects in Part 1a will be randomised to one of 3 treatments (A, B or C). The 24 subjects in Part 1b will be randomised to one of 2 treatments (D or E). Parts 1a and 1b may proceed in parallel, or may be done sequentially.

After at least 10 subjects have received each treatment in Part 1, and data up to 72 h after dosing are available, there will be a Dose Decision Meeting to determine which treatment(s) will be tested in Part 2 (see section 7.5).

In Part 2, either treatment F, G or both F and G will be tested. There will be 12 subjects enrolled for each treatment tested. If both treatments are tested, they will be done in parallel, and subjects will be randomised to one of the 2 treatments.

The study will be performed in a single site specialized in Phase 1 studies.

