3.4. Rationale of study design

The study will be performed in a randomized, open-label, parallel group design.

The open design of the trial has the important disadvantage that both investigator and subjects are aware that active treatment is being given, and there is no placebo. The possibility of bias must therefore be taken into account in the assessment of AEs in particular. However, the primary objective of the study is to compare the PK of emodepside after different formulations, which will be assessed using an objective test measured by an external laboratory. Relative bioavailability and food effect form part of the PK assessment. Most of the other assessments are also objective, either because they are measured by a laboratory or are measured using automated means (HR, BP, and ECG).

After a single dose, emodepside is rapidly absorbed and peak plasma concentrations occur within a few hours after dosing. There is a short half-life in the first 24 h

(distribution/elimination phase) followed by a long terminal elimination half-life ($t_{1/2}$ >500 h). Crossover designs are attractive because they can enhance the power of a trial to distinguish between treatments; that is because within-subject variability is generally less than between-subject variability. However, crossover designs are subject to carryover of effects from one treatment to the next, especially if the elimination half-life is long. Because of this, a parallel group design was chosen for this study and PK samples will be taken at the Follow-up Visit (168 h after dosing). Treatments in Part 1 will be randomized to reduce the likelihood of period or seasonal effects confounding the study assessments. Part 2 will also be randomized if both treatments are tested.

The study will be performed in healthy male Caucasian volunteers, in order to avoid ethnic and sex differences that may increase pharmacokinetic variability.

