4.3 Statistical Hypotheses

Except for the analysis of pharmacokinetic data, no formal statistical testing will be done.

5 Study Design

This is a single-centre, open-label, randomized, parallel-group relative bioavailability study in healthy men. The study will be done in 2 parts, as follows:

- Part 1 – single oral doses of 5 mg emodepside will be tested:
 - Part 1a – the LSF (reference formulation) and 2 new IR-tablet formulations (test formulations) will be administered in the fasted state.
 - Part 1b – the 2 new IR-tablet formulations will be administered in the fed state (high-fat, high-calorie meal).
- Part 2 – single oral doses of 10 mg (2 x 5 mg) emodepside will be tested: depending on the results from Part 1, one or both IR-tablet formulations will be administered in the fasted state.

The treatments in each study part are summarised in Table 1.

Table 1. Planned treatments by dose, formulation and condition

Part	Treatment	Formulation, dose and condition	Number of subjects
Part 1a	A	5 mg emodepside LSF, fasted	12
	B	5 mg emodepside IR-tablet #406, fasted	12
	C	5 mg emodepside IR-tablet #416, fasted	12
Part 1b	D	5 mg emodepside IR-tablet #406, fed	12
	E	5 mg emodepside IR-tablet #416, fed	12
Part 2	F*	2 x 5 mg emodepside IR-tablet #406, fasted	12
	G*	2 x 5 mg emodepside IR-tablet #416, fasted	12

* one or both treatments may be tested, depending on results from Part 1

Up to 84 healthy volunteers will be enrolled, in up to 7 treatment arms made up of 12 subjects each.

The 36 subjects in Part 1a will be randomised to one of 3 treatments (A, B or C). The 24 subjects in Part 1b will be randomised to one of 2 treatments (D or E). Parts 1a and 1b may proceed in parallel, or may be done sequentially.

After at least 10 subjects in each arm have received treatment in Part 1, and data up to 72 h after dosing are available, there will be a Dose Decision Meeting to determine which treatment(s) will be tested in Part 2 (see section 7.5).

In Part 2, either treatment F, G or both F and G will be tested. There will be 12 subjects enrolled for each treatment tested. If both treatments are tested, they will be done in parallel, and subjects will be randomised to one of the 2 treatments.

The study will be performed in a single site specialized in Phase 1 studies.

6 Time and Events Table

Procedure	Screening		Inpatient														Follow-up							
	Day -28 to -2	Day -1 hours	Day 0												Day 1		Day 2		Day 3		Day 5		Day 7	

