11.1 Data Display Treatment and Other Subgroup Descriptors

The sort order for treatment groups will be treatment in ascending dose order. When a total column is included, it immediately follows the treatment groups which it aggregates.

Listings of data will be sorted and displayed by treatment group, subject number, and also by date and time if applicable.

The treatment descriptions to be used on all tables and listings are:

Treatment Groups	Short Description
Emodepside LSF 5 mg [fasted]	LSF 5 mg [fasted]
Emodepside IR-tablet #406 5 mg [fasted]	IR #406 5 mg [fasted]
Emodepside IR-tablet #416 5 mg [fasted]	IR #416 5 mg [fasted]
Emodepside IR-tablet #406 5 mg [fed]	IR #406 5 mg [fed]
Emodepside IR-tablet #416 5 mg [fed]	IR #416 5 mg [fed]
Emodepside IR-tablet #406 10 mg [fasted]	IR #406 10 mg [fasted]
Emodepside IR-tablet #416 10 mg [fasted]	IR #416 10 mg [fasted]

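### F/A and G/A are judged against 80–125% as relative bioavailability, although they compare a 10 mg tablet in Part 2 with 5 mg LSF in Part 1a

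*SAP*

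**What the plan says.** SAP 15.2 and protocol 11.7 use one model for relative bioavailability: an ANOVA on log AUC0-7d/Dose or log Cmax/Dose, with formulation as the only fixed effect. B/A and C/A come from Part 1a. Then: "In Part 2, “F/A” and/or “G/A” will be calculated. The acceptance range 80 – 125% will be applied for these assessments".

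The treatment table (SAP Section 5, protocol 3.1) defines A as 5 mg LSF, fasted, Part 1a, and F and G as 2 x 5 mg tablets, fasted, Part 2. Part 2 has tablets only: "depending on the results from Part 1, one or both IR-tablet formulations will be administered in the fasted state". Protocol 7.2 uses LSF only for 5 mg doses, so there is no 10 mg LSF arm.

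Part 2 follows a decision meeting, which is held "After at least 10 subjects have received each treatment in Part 1, and data up to 72 h after dosing are available" (protocol 3.1). It is randomised only between F and G, and only if both are tested. On confounding, protocol 3.4 says: "Treatments in Part 1 will be randomized to reduce the likelihood of period or seasonal effects confounding the study assessments".

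Tablet linearity is a separate question in SAP 15.2: "To assess dose proportionality, for each tablet type, exploratory ANOVA models will be fitted to the relevant fasted data in Parts 1 and 2". F/B and G/C get a 95% CI there and no acceptance range. For the solution, protocol 1.4 reports that mean Cmax and AUC "for the LSF solution have been roughly dose-proportional".

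**The concern.** B/A and C/A can be read as formulation ratios because they are same-dose, randomised and within one part. F/A and G/A have none of these properties but carry the same criterion and the same name. Taking F and A alone, formulation, dose and study part change together, so a model with only a formulation term assigns all three effects to formulation. The plan leaves tablet linearity open and exploratory, yet sets a formal range on a ratio that contains it.

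At stake is how a primary-endpoint result is read. A pass or fail at 10 mg could be reported as a formulation finding when part of it is dose non-linearity or a difference between the parts.

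**Working it through.** **1. What F/A contains.** Let F, B and A be geometric means, A10 the unobserved mean for 10 mg LSF, and s any Part 2 to Part 1 shift. On the dose-normalised scale:

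- F/A = (5 mg ratio B/A) × (tablet 10:5 mg linearity factor) × s. The last two factors together are the planned F/B divided by 2.
- F/A = (10 mg ratio F/A10) × (LSF 10:5 mg linearity factor, A10/(2 × A5)) × s.

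So the 5 mg reading needs tablet linearity, the 10 mg reading needs LSF linearity, and both need s = 1, unless the effects happen to cancel. B/A identifies the formulation effect at 5 mg. F/B and G/C cross the same two parts, so they cannot separate dose from part.

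**2. Inputs (protocol 3.4, first-in-human LSF).** The plan gives no power or expected ratio to reproduce. Its CVs do reproduce from SD/mean.

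| | 5 mg mean (CV) | 10 mg mean (CV) | per mg | 10:5 mg ratio |
|---|---|---|---|---|
| AUClast | 1736.2 (22.6%) | 3165.2 (25.8%) | 347.2; 316.5 | 0.912 |
| Cmax | 93.2 (16.8%) | 178.6 (26.8%) | 18.64; 17.86 | 0.958 |

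Converted to geometric means by mean/√(1+CV²), the ratios are 0.905 and 0.938. With 6 subjects at 10 mg and 5 or 6 at 5 mg (protocol 1.4), the approximate 90% CIs for these geometric ratios are at widest 0.69 to 1.18 (AUC) and 0.74 to 1.19 (Cmax). Both include 1. At 20 mg the AUC ratio to 5 mg is (7617.0/20)/347.2 = 1.097, so AUC shows no consistent trend.

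**3. Room for error.** Log-SD σ = √ln(1+CV²); the 90% CI half-width is h = t(0.95; 22) × σ × √(2/12), with t = 1.717. At CV 22.6%, σ = 0.2232, h = 0.1565 and e^h = 1.169. The point estimate must then lie between 0.80 × 1.169 = 0.94 and 1.25/1.169 = 1.07. The window is 0.90 to 1.11 at CV 16.8% and 0.96 to 1.04 at CV 26.8%.

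**4. Chance of passing, 12 per arm, tablet identical to LSF.** Two-group log-normal comparison, same CV in both arms, 90% CI inside 80–125%.

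| | No dose or part effect | First-in-human ratio applied |
|---|---|---|
| AUC, CV 22.6% | 53% | 36% (0.912) |
| AUC, CV 25.8% | 34.5% | 24% (0.912) |
| Cmax, CV 16.8% | 87% | 80.5% (0.958) |
| Cmax, CV 26.8% | 29% | 27% (0.958) |

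With the 5 mg CV in arm A and the 10 mg CV in arm F, the figures are 43% and 30% (AUC), and 55% and 50% (Cmax).

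**5. The other direction.** Take a true same-dose ratio of 0.75 and an assumed combined dose-and-part factor k, at CV 22.6% with 12 per arm. The expected F/A is 0.75k. The chance of passing is 1% at k = 1, 9% at k = 1.1 and 31.5% at k = 1.2. The documents give no value for k.

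**The case against.** The case for leaving the plan alone is substantial. The study calls itself exploratory and has no formal sample size. LSF is described as roughly dose-proportional, which supports dose normalisation for the 10 mg reading. Both parts share one site, the same entry criteria, fasting rules and sampling schedule, within about 6 months, and no mechanism for a part shift is apparent. B/A and F/B are both to be reported, so a careful reader can see how far F/A departs from B/A.

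Most of this limits the size of the problem without removing it. Rough proportionality of LSF does not speak to tablet linearity. Reporting F/B beside F/A does not isolate dose from part, and with 12 per arm its 95% CI spans about ×/÷ 1.15 to 1.25 (CV 16.8% to 26.8%). The randomisation that protocol 3.4 relies on against period effects does not reach a ratio across parts.

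Three stronger readings are tempting and are not supported:

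- *The first-in-human data show non-linearity.* They do not. The intervals include 1, AUC is not monotone, and the data are LSF and AUClast, not tablets and AUC0-7d.
- *The trial cannot identify a formulation effect.* It can, through B/A and C/A at 5 mg.
- *The source of the reference is concealed.* Treatment A is plainly defined as Part 1a, and the SAP 11.1 treatment descriptions show the LSF dose. At most, the Part 2 table shell lacks a note.

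**Conclusion.** The concern holds. The 80–125% criterion on F/A and G/A yields a formulation verdict that also contains any 5 to 10 mg non-linearity and any difference between the parts, and neither assumption is stated for these ratios.

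The size is moderate and only illustrative. If the first-in-human LSF ratios applied, the chance that an identical tablet passes would fall by about 10 to 18 percentage points for AUC and 2 to 7 for Cmax. Even with no such effect, that tablet fails 47% to 65% of the time on AUC and 13% to 71% on Cmax, so small arms and between-subject variability account for most of the failure risk. A combined effect in the favourable direction could raise the chance of a false pass materially, but its size is an assumption.

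These figures rest on log-normal data, 12 evaluable subjects per arm and first-in-human CVs carried over to the tablets. B/A, C/A and the choice of Part 2 treatment are unaffected.

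**What to change.** In SAP 15.2 and protocol 11.7, apply the 80–125% relative-bioavailability criterion to B/A and C/A only. Keep F/A and G/A with their 90% CIs as descriptive results, labelled: *10 mg tablet (Part 2) vs 5 mg LSF (Part 1a), non-randomised, non-concurrent; assumes dose linearity and no part effect*. Repeat that label in the Part 2 version of template T_PK6, because SAP 7.2 has the parts reported separately and the Part 2 tables will be read on their own.

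No new data or subjects are needed. The sponsor gives up a formal acceptance statement at 10 mg. Because the ratios analyse the primary endpoint, a protocol amendment may also be needed: protocol Section 11 requires one for major changes to that analysis. Stating the assumptions while keeping the range would cost less, but would leave a formal pass or fail resting on conditions that the design cannot check separately.
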